Scientists and health providers are currently limited in their knowledge of all of the biopsychosocial processes that constitute a pain experience. Pain perception is influenced by, and modulated through, processes that involve tissue stress and damage (e.g., physical disease and injury), peripheral and central nociception (i.e., afferent input and brain processing), mental thoughts (e.g., memories), emotions, and social settings (e.g., Gatchel, Peng, Peters, Fuchs, & Turk, 2007; McCaffery & Pasero, 1999). Although significant progress has been made in investigating many of these processes (e.g., opioid reception), we still do not fully understand how certain aspects of pain experiences operate, including the role of endogenous steroids on the behavioral demonstration of pain. It is wellestablished that biological sex modulates pain. As compared to males, females report greater prevalence, frequency, and duration of clinical pain and pain-related distress (Unruh, 1996; Berkley, 1997; Fillingim, Edwards, & Powell, 2000; Riley, Robinson, Wise, Myers, & Fillingim, 1998; Ruau, Liu, Clark, Angst, & Butte 2012). Experimental studies show that women are more likely to report lower pain threshold and tolerance, and higher pain intensity associated with various types of noxious stimuli (e.g., ischemic, pressure, electrical, and thermal; Berkley, 1997; Fillingim, Edwards, & Powell, 2000; Riley, Robinson, Wise, Myers, & Fillingim, 1998; Fillingim, & Maixner, 1996; Shinal & Fillingim, 2007; [name] & Coulombe, 2011). The magnitude of these effects varies from moderate to large depending on sample size, nature of the stimulus, and whether pain sensitivity is indexed by threshold or tolerance (Berkley, 1997Riley, Robinson, Wise, Myers, & Fillingim, 1998; Shinal & Fillingim, 2007, Fillingim, King, Ribeiro-Dasilva, Rahim-Williams, & Riley, 2009). It is generally assumed that gonadal sex hormones contribute to greater clinical and experimental pain experiences in women as compared to men (Fillingim, King, Ribeiro-Dasilva, Rahim-Williams, & Riley, 2009; Kuba & Quinones-Jenab, 2005; Riley, Robinson, Wise, Myers, & Fillingim, 1998; Ruau, Liu, Clark, Angst, & Butte, 2011; [name] & Coulombe, 2011). Among the potential endocrine substrates responsible for gender differences in pain sensitivity is testosterone, an androgen produced primarily in the testis in males. Testosterone has been linked to several behaviors that prepare, motivate, and otherwise promote exposure to environmental dangers that result in pain experiences in vivo. Previous research with animal models and humans has found that individuals with higher levels of testosterone tend to be on average more aggressive and perform riskier behaviors than individuals with lower levels of testosterone (Beeman, 1947; Albert, Walsh, Gorzalka, Siemens, & Louie, 1986; Hume, & Wynne-Edwards, 2005; Stenstrom, Saad, Nepomuceno, & Mendenhall, 2011; Vermeersch, T'Sjoen, Kaufman, & Vincke, 2008; Booth, Johnson, & Granger, 1998). Studies looking at competition have found that humans that succeed in a competitive tasks (e.g., wrestling, tennis, stock-trading) had higher levels of testosterone and lower levels of the stress hormone cortisol than the losers of these tasks (Coats & Herbert, 2008; Mazur & Lamb, 1980; Elias, 1981). Dominant males in several primate groups have been found to have higher testosterone and lower cortisol than submissive males (Rose, Holaday, & Bernstein, 1971; Muller & Wrangham, 2004). Therefore, it has been assumed that testosterone has been linked to prototypical male behaviors such as aggression, risk taking behaviors, competition, and dominance.

Experimental studies in females has found that women with higher basal levels of testosterone show higher levels of what are generally considered protypical male behaviors, and repeated experiments have replicated similar effects. For example, a study looking at dominance in females found that females with high levels of testosterone attributed more dominant characteristics to themselves than women with lower levels of testosterone (Grant & France, 2001). Female twins with a male twin brother show higher mean levels of aggression than same-sex, female twins, and this has been attributed to testosterone exposure in the womb (Cohen-Bendahan, Buitelaar, van Goozen, Orlebeke, & Cohen-Kettenis, 2005). Under controlled laboratory conditions, females that are given low doses of testosterone show reductions in empathetic behaviors (Hermans, Putman, & van Honk, 2006; van Honk, Schutter, Bos, Kruijt, Lentjes, & Baron-Cohen, 2013; Montoya, Terburg, Bos, Will, Buskens, Raub, van Honk, 2013). A logical extension of the above described work as it relates to sex differences in pain perception is to use a controlled laboratory experiment to examine how ephemeral and thus safe, short-lasting testosterone induction interacts with naturally circulating basal levels of testosterone to influence external pain sensitivity as part of a broad spectrum of changes in social behaviors associated with fluctuating testosterone levels.

OBJECTIVES/AIMS/HYPOTHESES

Our hypotheses are that: a) Females with high levels of circulating salivary (basal) Testosterone levels will experience reduced pain tolerance (hypoanalgesia) in a ischemic pressure pain task (primary outcome); b); Testosterone will alter the participants basal levels of estradiol and progesterone (secondary outcome) c): Further, exploratory outcomes will test whether testosterone will increase risk-taking behaviors, aggression, perception of health, attractiveness, disgust response, and sexual attitudes and beliefs.

STUDY DESIGN AND PROCEDURES

I. Study Design

The first part of the experiment will: a) examine basal levels of testosterone in females b) measure baseline pain tolerance) experimentally manipulate ephemeral (short-lasting) testosterone levels in females. The second part of the experiment takes place 4 hours later and consists of a pain task and behavioral measures/tasks. A double-blind protocol will be used so neither the researchers nor participants will know whether the participants were in the testosterone group or the placebo group until after the experimental procedures have been completed.

II. Study Procedures

Main Procedure

The proposed study will consist of 2 experimental sessions where each participant will spend at most 5 hours per session. Prospective participants who meet our initial inclusionary criteria will come to the lab for a prelab session (See Appendix: Flow Chart of Experimental Procedures that Will Occur Over 4 Days for Each Participant). This session will be used to explain to the participants about the risks and benefits of participating in this study and to make sure they understand the time commitment. Once the prospective participants have read and stated they understand what is required of them, they will be allowed to sign the consent form and schedule their first lab visit. All lab visits will be determined based on the participant's menstrual cycle (See Appendix: Menstrual Cycle Scale). All female participants will visit the lab during their luteal phase of their menstrual cycle. The second lab visit will be 3 days after the first to ensure that the female participants are still in their luteal phase during the second lab visit. This will ensure that the changes in behavior and in pain are not the result of variations of within the menstrual cycle. At their first lab visit, participants will be pre-screened for pregnancy, tree nut allergies, and any use of drugs (e.g., Insulin, Blood-Thinners, Corticosteroids, Oxyphenbutazone, Triamcinolone) that may negatively interact with testosterone. After the first session, female participants will continue to be screened for pregnancy via a pregnancy test. Females who do test positive for pregnancy will be excused from the experiment and will be referred to the UNM Student Health and Counseling Center (SHAC) where they can seek further care. All participants will be inquired about any new medication use before the start of each session. Because exercise, sexual behaviors, and competitive activities may increase testosterone, all participants will be instructed to avoid these activities on the days that they participate in the experiment. Participants will also be asked to report the time they woke up in the morning to control for fluctuations in testosterone over the course of the day.

Participants will be randomly assigned to either a placebo group or a testosterone group before arrival. The experimenters will be blinded to this assignment. Randomization of the placebo and experimental drugs will be controlled by the research pharmacist.

Participants will provide an initial salivary sample to establish baseline testosterone levels. Once they have given this sample, the participants will be given either the placebo or testosterone. They will then provide saliva samples 15 mins following the intervention. This will establish an intervention check. Baseline saliva sample before and after each intervention will be provided. Participants will remain in the lab for the duration of

this 5-hour session. They will be allowed to watch Netflix and listen to music as they wait. However, the content they can view or listen to will be limited to G or PG ratings in order to avoid fluctuation in their testosterone level. Participants will also be instructed to turn their cell phones off to ensure that their mood is not significantly altered. At 4 hours, participants will complete the post administration pain task. This pain task, like the behavioral measures, will only be administered once after 4 hours has passed. This is to prevent contamination and practice effect, which can occur when a behavioral task or measurement is administered multiple times during a session. The experimental sessions will take place 3 days apart. Participants will be reminded about their informed consent before their second session to ensure that they understand their continued rights as a research participant across the 2 experimental sessions. Participants will be awarded 3 research credits for each session for a total of 6 research credits. Participants will also be paid \$5 after completing each session for a total of \$10 for their participation.

Saliva Samples

Each participant will be given a saliva oral swab for saliva collection. Participants will be instructed to lightly chew on the cotton swab for 1 min. At the end of this time, participants will be instructed to place the swab in a test tube where it will be stored in our lab freezer. These saliva samples will be labeled with the participant's subject number. Three hormones will be assessed from the participant's saliva: testosterone, estradiol, and progesterone. An enzyme-linked immunosorbent assay (ELISA) diagnostic tool will be used to assess the specific level of each of these hormones at Hominoid Reproductive Ecology Laboratory located on UNM Main Campus. Measurement of testosterone using salivary samples has been found to be a reliable methods of assessing hormonal levels of individuals and has been used for diagnoses of endocrine dysfunctions in both males and females (Shirtcliff, Granger, & Likos, 2002; Morely, Perry, Dollbaum, & Kells, 2006; Cardoso, Contreras, Tumilasci, Elbert, Aguirre, Aquilano, & Arregger, 2011; Karrer-Voegeli, Rey, Reymond, Meuwly, Gaillard, & Gomez, 2009). Three hormones will be assessed in these analyses: testosterone, estradiol, and progesterone. Once these samples have been processed, they will be disposed of by the lab.

Testosterone Administration

The drug will be attained from the UNM Research Pharmacy that will prepare both the placebo and the drug for the purposes of this study (See Appendix: Letter from Research Pharmacist). The researchers will be blinded to this study. On the day of the experiment, the medical doctor on staff will write an individual prescription for the subjects participating in the study that day. The researchers conducting this study will then present the prescriptions to the UNM Research Laboratory and pick up the drug for the purposes of this study. Each subject will have an individual syringe prepared for them in which they will self-administer with directions from the researchers of this study. When the drug/placebo is in the lab it will be secured in a locked cabinet in our lab facilities; however, only testosterone/placebos being used for that days session will be stored at our lab . Only authorized lab personnel and/or medical personnel will have access to the drug at any time and a log will be kept indicating the inventory of the drug and when the drug has been removed from the cabinet and used. In the case that an unauthorized removal of the drug occurs (i.e. theft) or if there is indication that the log has been fabricated, the IRB will be notified immediately.

Participant Safety. Previous research has established that the current protocol will increase circulating levels of testosterone in the body by a factor of 10 within 15 mins of administration with baseline levels of testosterone returning to normal in 1.5 hrs after administration. As noted, however, behavioral effects of .5 mg of Testosterone reach their maximum levels 3-4 hours after administration (Tuten, van Honk, Koppeschaar, Bernaards, Thijssen, & Verbauten, 2000). Several studies using this same procedure for administration for Testosterone have found it to be a safe and effective means of administration for women with no ill effects or complications being reported by the authors as described in the form in the Appendix called "Table of Past Studies" (van Honk, Schutter, Bos, Kruijt, Lentjes, & Baron-Cohen, 2011; Montoya, Terburg, Bos, Will, Busken,

Raub, & van Honk, 2013; Hermans, Putman, & van Honk, 2006). We consulted a medical doctor about the dosage we intend on administering and they confirmed that the amount we will administer is safe, miniscule, and should not cause any long term issues with the participants (See Appendix: Letter from Medical Doctor). Subjects will be notified of the side-effects of more potent, repeated hormonal medication therapy which include: stomach or bowel complaints, acne/skin irritation, sleeplessness, chills, headache, anxiety, mental depression, excitation, confusion, dizziness, muscle pain, prolonged abnormal erection, inflamed testies, bladder, sexual dysfunction, prostatic growth, high blood pressure, blood disorders, shortness of breath, fluid retention, breast enlargement, and changes in liver function. However, the amount of testosterone we will be administrating is very low when compared to a typical dosage used for androgen replacement therapies (e.g., 40 mg to 300 mg) and will only be administered once. Further, previous studies show that potential complications associated with this drug are very minimal (see Table of Past Studies in Appendix). This same method was used in a previously approved protocol at UNM (IRB Approval Code: 902016-3). None of our participants reported any complications or side-effects from receiving the testosterone. Known medications that negatively interact with this form of Testosterone are: barbiturates, antidiabetic drugs, cyclosporine, Insulin, and anti-coagulants. Subjects will provide information on the medications they are currently taking in order to avoid these potentially harmful interactions.

Ischemic Discomfort Task

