> Anyone that has a tree nut allergy. Females that are pregnant or may feel that they may be pregnant or breast-feeding. Anyone taking supplements that may influence their testosterone level. Anyone taking any kind of steroid that may increase his or her testosterone level. Anyone that smokes tobacco or uses smokeless tobacco. Anyone that reports any condition associated with nerve damage. Anyone that is using hormonal contraceptive.

Each participant will complete a Testosterone Pre-Screen form (see Appendix). This form will ask each participant individually whether they are taking any drugs or have any conditions that might be exacerbated by testosterone. This form will be completed before they participate sign the consent form and each time they arrive in the lab for an experimental session.

- II. Participant Enrollment Twenty Female Participants will be enrolled in this study.
- III. *Recruitment and Screening Procedures* Participants will be recruited via the UNM Psychology SONA system.
- IV. Informed Consent Process

The participants have several opportunities to decide whether to continue or to terminate their involvement. Solicitations will operate through the SONA system, in which prospective participants are fully informed of the study protocol. All participants will attend a pre-lab session where only the consent form will be discussed. The experimenter will go through the consent form and make sure that the participant understands all that is required of them before they sign the consent form. Students will thus be allowed up to two weeks prior to a scheduled start date to decide whether they would like to participate in this study. I am also freely available to answer questions and concerns. Prior to their involvement in the study (upon arrival to the study location), participants are expected to provide written consent for the overall study (See Consent Form).

V. Data Collection Procedures

Described above in the Main Experiment Procedure. Two saliva samples will be collected during each of the 2 sessions that each subject attends:

- 1. Pre-Experiment saliva
- 2. Post Testosterone administration at 15 mins

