Data analysis will be conducted using Multilevel Modeling to examine any potential differences across the experimental conditions. The pilot study used 12 participants. A power analysis was not carried out on the pilot study data due to the complication of conducting a power analysis using multilevel modeling. However, a prior power analysis conducted using the effect size reported in Chen, Decety, Huang, Chen, and Cheng (2016) used similar methods. Using these reported effects a sample size of 15 was adequate to find a significant effect with a power of 0.80 and an alpha of 0.05. The findings in the power analysis and the results from the pilot study, highly suggest that 15 participants will be sufficient in capturing significant results.

Participant Withdrawal

Subjects who decide to not participate in the study or who are otherwise ineligible for participation in the experimental protocol will be given the option to write a 5 page essay for the equivalent of 6 hours of research credit (for instructors who accept such credit).

Due to the expense and the complication of this study, if participants choose to withdraw, the researchers will process the biological samples and psychological data that were collected from the participants. This data will be used in subsequent analyses for this study. However, upon withdrawal if the participant would not like their biological or psychological data to be used for this study: they will be instructed to inform either the research assistants or the Principle Investigator for this study and their data will be excluded and their biological samples and psychological data will be destroyed.

PRIOR APPROVALS/REVIEWED AT OTHER IRBS

n/a

REFERENCES

Albert, D. J., Walsh, M. L., Gorzalka, B. B., Siemens, Y., & Louie, H. (1986). Testosterone removal in rats results in a decrease in social aggression and a loss of social dominance. *Physiology & behavior*, *36*(3), 401-407.

Beeman, E. A. (1947). The effect of male hormone on aggressive behavior in mice. *Physiological Zoology*, 373-405.

Berkley, K. J. (1997). Sex differences in pain. *Behavioral and Brain Sciences*, 20(03), 371-380.

Birnie, K. A., Noel, M., Chambers, C. T., von Baeyer, C. L., & Fernandez, C. V. (2010). The cold pressor task: Is it an ethically acceptable pain research method in children?. *Journal of pediatric psychology*, jsq092.

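### Wake-up time is collected to control for daily testosterone drift, but the available text fixes no session hour or saliva clock time and gives wake-up time no place in the analysis, so the control is not delivered as written

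*Combined protocol and SAP*

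**What the plan says.** - **Purpose of wake-up time.** Under Study Procedures, Main Procedure, participants are asked to "report the time they woke up in the morning to control for fluctuations in testosterone over the course of the day". The same section restricts activities thought to raise testosterone on study days, so stability of the reading is a declared aim.
- **Scheduling.** "All lab visits will be determined based on the participant's menstrual cycle". Both visits fall in the luteal phase, 3 days apart. No hour of day is given.
- **Sampling.** V. Data Collection Procedures: "Two saliva samples will be collected during each of the 2 sessions", one before dosing and one 15 minutes after. These times are relative to the dose. Under Saliva Samples, "These saliva samples will be labeled with the participant's subject number"; no collection time is mentioned.
- **Use of the basal reading.** Hypothesis (a), tied to the primary outcome: "Females with high levels of circulating salivary (basal) Testosterone levels will experience reduced pain tolerance".
- **Analysis.** II. Data Analysis/Statistical Considerations: "Data analysis will be conducted using Multilevel Modeling to examine any potential differences across the experimental conditions". No covariate is named.
- **A possible indirect record of time.** Under Testosterone Administration, "a log will be kept indicating the inventory of the drug and when the drug has been removed from the cabinet and used".

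**The concern.** The plan accepts that testosterone moves through the day and sets out to control for it, but collects only half of what is needed. Two women who both wake at 07:00, one sampled at 08:00 and the other at 13:00, report the same wake-up time and are 1 hour and 6 hours past waking. Wake-up time cannot separate them without the sampling time.

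This touches the primary hypothesis directly, because hypothesis (a) uses the basal level itself as the predictor. Testing pain 4 hours after dosing does nothing to clean that earlier reading. At stake are the strength of the observed association, the power to detect it, and the comparability of a participant's two baselines should her two visits start at different hours.

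**Working it through.** **1. Is the control operational?** Time since waking = sample clock time − wake-up time. The second term is collected. For the first, the available text offers a menstrual-phase rule, sample times relative to dosing, and a subject-number label, none of which gives an hour. The analysis section would also need a term using the result, and it has none.

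**2. The plan's own figure.** The plan states that 15 participants give power 0.80 at alpha 0.05, using an effect size from a cited study. The effect size, standard deviation, test and sidedness are not given, so 15 cannot be reproduced. Read as a correlation (two-sided, Fisher z), it implies r = tanh((1.960 + 0.842)/√(15 − 3)) = tanh(0.809) = 0.669. That is a back-solved value, not the sponsor's.

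**3. Illustration of the loss.** From the documents: n = 20 enrolled and alpha 0.05. Assumed: a two-sided test, a true correlation ρ = 0.6, a share s of the variance of one basal reading that is time-of-day, and timing error unrelated to both the true basal level and pain tolerance.

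- Observed correlation: r = ρ√(1 − s)
- Power: Φ(atanh(r)·√(n − 3) − 1.960), with √17 = 4.123

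| s | √(1 − s) | r | atanh(r) | power |
|---|---|---|---|---|
| 0 | 1.000 | 0.600 | 0.693 | 0.815 |
| 0.1 | 0.949 | 0.569 | 0.646 | 0.760 |
| 0.2 | 0.894 | 0.537 | 0.599 | 0.696 |
| 0.4 | 0.775 | 0.465 | 0.503 | 0.546 |

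**4. Sensitivity to the assumed correlation (n = 20).**
- ρ = 0.669: power 0.915 with no timing error; 0.870, 0.812 and 0.658 at s = 0.1, 0.2 and 0.4.
- ρ = 0.4: power 0.42 with no timing error and 0.34 at s = 0.2. Here sample size is the larger problem.

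**5. If the two pre-dose samples are averaged.** With independent timing errors, the error variance halves and reliability becomes (1 − s)/(1 − s/2) = 0.947, 0.889 and 0.750. At ρ = 0.6, r = 0.584, 0.566 and 0.520, and power = 0.79, 0.75 and 0.66. The largest loss shrinks from 0.815 − 0.546 = 0.27 to 0.815 − 0.661 = 0.15. The plan does not say that the samples will be averaged.

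**6. Cost of the covariate.** One adjustment term changes √(n − 3) to √(n − 4) = 4. At ρ = 0.6 (taken as the partial correlation), power = Φ(0.693 × 4 − 1.960) = Φ(0.813) = 0.79. If the covariate removes the timing error, that compares with 0.76, 0.70 or 0.55 unadjusted on a single reading.

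**The case against.** - **The sampling time may be recoverable.** The drug log is to show when drug is used, and dosing follows the baseline sample: "Once they have given this sample, the participants will be given either the placebo or testosterone". Later steps are timed from dosing, so staff must track it. A reader might infer that wake-up time can never serve its purpose; the documents do not support that. What stands against the objection is that the plan does not say whether the log holds clock times or only dates, and does not connect it to the analysis.
- **Part of the plan is not in view.** The flow chart, the pre-lab survey on testosterone-related behaviours and the pre-screen form are listed in the Appendix but are not in the available text. Any of them might hold a start hour or a collection time. The absence is therefore shown only for the available text.
- **The analysis section names no covariate at all, not even basal testosterone.** True: wake-up time is one symptom of a thin section. But it is a variable with a declared purpose and no planned use, and a sampling time not recorded during conduct may not be recoverable afterwards.
- **Dilution toward zero is not certain.** The pain task is fixed at 4 hours after dosing, so session hour shifts predictor and outcome together. If pain tolerance also varies by hour, the bias could go either way. This stands and is carried into the conclusion.
- **The randomised comparison is unaffected.** A reader might infer that the testosterone-versus-placebo contrast is biased. It is not: assignment is random, so error in the baseline reading does not bias that contrast. The point concerns the basal-level hypothesis.
- **Different hours for one woman's two visits are conjecture.** The documents neither state nor exclude this.

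**Conclusion.** The point holds in a limited form. The plan states a purpose for wake-up time; the available text provides neither a clock time or start hour to combine with it, nor a model term that uses it. Followed as written, the intended control does not reach the basal testosterone reading in hypothesis (a), though an approximate sampling time may be recoverable from the drug log.

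The direction of the effect, a weaker association and lower power, rests on timing error being unrelated to pain tolerance. Its size cannot be derived from the documents: the 10% to 40% shares and the correlation of 0.6 are assumptions, and the calculation treats hypothesis (a) as a single correlation rather than the planned multilevel model. The figures show that the loss could matter at this sample size, not that it will. Nothing here invalidates the trial or raises a safety issue. It is a cheap improvement.

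**What to change.** 1. Record the clock time of each baseline saliva sample.
2. Start a participant's two sessions at the same hour.
3. Prespecify time since waking (sample time minus wake-up time) as a covariate in the model that tests basal testosterone against pain tolerance. The analysis section will have to write that model out, and should say there whether the two pre-dose readings are averaged or used separately.

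If the flow chart or forms already fix the hours or record collection times, a cross-reference covers the first two items and only the model term remains.

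Cost: one recorded time per session, a scheduling constraint on top of the luteal-phase and 3-day rules, and one degree of freedom.
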